8.2 Participant Training, Device Dispensing, and Home Use

On Day 0, participants will be provided with a TrueTear and disposable tips to take home with them and use daily per the Instructions for Use (IFU). Participants will receive training to perform intranasal neurostimulation and will receive a user guide. Following device training and prior to entering the CAE, devices for home use will be dispensed to participants. The serial number of the unit and the lot number of disposable tips will be documented in the participant's CRF.

Participants will undergo stimulation for the first time on Day 0 during the CAE session where they will be instructed to apply stimulation for approximately three minutes. Training will include instruction on the following points:

- Between study visits, participants will be asked to perform neurostimulation at least two times per day up to as many as 10 times per day, as needed. Each stimulation should last no longer than three minutes. Participants should be instructed that the device has a single-day stimulation limit of 30 minutes at which point the device will time-out.
- Participants will be asked to fully charge the device before first use and to re-charge daily.
- After using the device, participants will be instructed to clean the system with tissue or an alcohol pad if necessary prior to placing the cover to protect the tip between uses.
- Participants should be instructed to replace the disposable tip daily according to the IFU and that the used tip should be discarded in trash.

For the device application, participants will be instructed to place the tips of the TrueTear into both nostrils simultaneously towards the top and front of the nose (as in [Figure 2](#)). They will be told to turn on the unit by holding down the + button for approximately two seconds. There are five stimulation intensity levels and participants may adjust the level by pressing the + or – buttons to obtain a gentle tingling sensation. Participants will be told they can cease stimulation by holding down the – button for approximately two seconds on the base unit or by withdrawing the tips from the nostrils. Participants will be instructed to replace the Tip if they do not feel any sensation.

Figure 2 Use of the TrueTear

(L) Starting position and (R) Correct application position by inserting the disposable tips fully into the nasal cavity and to the front of the nose.

At Visit 3 (Day 7), prior to in-office application and evaluation of tear secretion, trained clinical personnel will review procedures for the proper use of the device (e.g., correct positioning intranasally, frequency and duration of use, daily replacement and disposal of tips, etc.) with participants.

Note: A Sponsor representative may be present at visits to assist in training participants on the use of the device.

8.3 Concurrent Therapies

The use of any concurrent medication, prescription or OTC, is to be recorded on the participant’s CRF along with the reason the medication was taken. Concomitant medications that are considered necessary for the participant’s welfare, but will not interfere with study assessments and evaluations, will be allowed during the study at the Investigator’s discretion.

Concurrent enrollment in another investigational drug or device study is not permitted.

8.4 Examination Procedures

The following procedures will be performed (see [Appendix 2](#) for description):

8.4.1 Procedures to be Performed at the Screening Visit (Visit 1; Day -21 ± 20)

Review of qualification criteria should take place with each test that relates to eligibility.

- [REDACTED]
- [REDACTED]
- [REDACTED]

- [Redacted]
- [Redacted]
- [Redacted]
- [Redacted]
- [Redacted]
- [Redacted]
- [Redacted]
- [Redacted]

8.4.2 Procedures to be Performed on the Day 0 CAE Visit (Visit 2; Day 0)

- [Redacted]
- [Redacted]
- [Redacted]
- [Redacted]
- [Redacted]

- Approximately 120 minutes of CAE exposure

- [Redacted]
- [Redacted]
- [Redacted]
- [Redacted]

[Redacted]

- [Redacted]
- [Redacted]
- [Redacted]
- [Redacted]

8.4.3 Procedures to be Performed on Tear Production Assessment Visit (Visit 3; Day 7 ± 2)

- [Redacted]

8.4.4 Procedures to be Performed on Day 45 CAE Visit (Visit 4; Day 45 ± 7)

- [Redacted]
- [Redacted]
 - [Redacted]
 - [Redacted]
 - [Redacted]

[REDACTED]

8.4.1 Early Termination/Discontinuation

If a participant is discontinued from the study prior to Visit 4, then all safety evaluations and Pre-CAE evaluations that are to be performed should be completed on the day of discontinuation (early termination) with the participant's agreement.

8.5 Schedule of Visits

8.5.1 Scheduled Visits

Participants will remain in the study for approximately 66 days and will be seen at the following intervals:

Visit 1	Screening Visit (Day -21 ± 20)
Visit 2	Day 0 CAE Visit (Day 0)
Visit 3	Tear Production Assessment Visit (Day 7 ± 2)
Visit 4	Day 45 CAE Visit (Day 45 ± 7)

The schedule of exams and procedures performed at these visits can be found in [Appendix 1](#). Descriptions of exams and procedures performed during these visits can be found in [Appendix 2](#).

Participants who are exited from the study due to unanticipated adverse device effects (UADEs) will be followed until their medical outcome is determined. The Investigator should provide written reports about the status of UADEs to the study Sponsor.

8.5.2 Unscheduled Visits

These visits may be performed in order to ensure participant safety. For participants reporting for an unscheduled visit, assessments performed are at the discretion of the Investigator. At minimum, AEs should be assessed. All procedures performed at an unscheduled visit will be recorded on the Unscheduled Visit CRF. Any procedure indicated in the CRF that is not performed should be indicated as “Not done.”

8.6 Completed Participants

A completed participant is one who has not been discontinued from the study and has successfully completed Visit 4.

8.7 Study Termination

The study may be stopped at any time by the Investigator, the Sponsor, and/or [REDACTED] with appropriate notification.

8.8 Study Duration

An individual participant’s participation will involve up to four visits over an approximate 66 day period.

8.9 Monitoring and Quality Assurance

8.9.1 Study Monitoring

Allergan personnel (or designees) will monitor this study in a manner consistent with applicable health authority regulations and the procedures adopted by the SOPs of the Sponsor, Allergan. Prior to the start of the study, member(s) of Allergan and/or [REDACTED] (or designees) will review the protocol, CRFs, regulatory obligations, and other material or equipment relevant to the conduct of the study with the Principal Investigator/Sub-Investigator(s) and pertinent study staff. Monitoring visits will occur as necessary during the course of the investigation to verify:

- The rights and well-being of participants are protected
- The conduct of the investigation is in compliance with the currently approved protocol/amendment, GCP and IRB/IEC requirements
- The integrity of the data
- Study device accountability
- Adequate study documentation

During the course of the study, if the Sponsor (or designee) determines that the Investigator is non-compliant with the study plan and/or applicable regulatory requirements, the Sponsor (or designee) will take written action to correct the non-compliance and to secure compliance. In addition, the Sponsor (or designee) may terminate the Investigator's participation in the study if appropriate, or if the Investigator remains non-compliant despite the Sponsor's actions. This termination will be documented in a memo or follow-up letter to the Principal Investigator.

8.9.1 Recording of Data

Participant data recorded on CRFs during the study will be documented in an anonymous fashion. The participant will only be identified by the participant number. If, as an exception, it is necessary for safety or regulatory reasons to identify the participant, the Sponsor or its representatives, and the Investigator, are bound to keep this information confidential.

9.0 ADVERSE EVENTS

An AE is defined as any unfavorable and unintended sign (including an abnormal laboratory finding) symptom, or disease temporally associated with the use of an investigational product but not necessarily related to the investigational product. An AE may also be called a complication. The capture of AEs will begin with the participant's entry into the CAE.

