9.6 Anticipated Adverse Events

The following is a list of potential AEs associated with the use of the device:

- Nasal discomfort or pain
- Epistaxis
- Excessive sneezing
- Nasal irritation, paresthesia or numbness post-stimulation
- Nasal infection, abrasion or inflammation
- Skin irritation or hypersensitivity
- Headache (e.g., tension, migraine, etc.)
- Facial pain
- Excessive salivation
- Sensation of teeth vibrating
- Excessive rhinorrhea
- Temporary aggravation of nasal allergies
- Allergic reaction to contact materials

The following is a list of potential AEs associated with the testing procedures at Screening or with CAE exposure:

- Ocular discomfort
- Moderate or severe conjunctival injection
- Clinically significant decrease in visual acuity
- Clinically significant increase in corneal or conjunctival epithelial defects
- With use of proparacaine, temporary burning, stinging and conjunctival redness of the eyes
- With use of proparacaine, a rare hyperallergic corneal reaction characterized by epithelial keratitis, sloughing of epithelium, corneal filaments and iritis
- With the Schirmer test, corneal irritation and abrasion
- Allergic reaction to contact materials

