15.2.4 Basal Schirmer Test with Topical Anesthesia

The Schirmer test with topical anesthesia will be used to assess tear production using the following steps:

1. One drop of topical anesthetic such as 0.5% proparacaine hydrochloride or equivalent should be instilled in each eye of the participant.
2. The participant will be instructed to keep the eyes gently closed for one minute.
3. After opening the eyes and allowing the eyes to recover for approximately one additional minute, excess moisture in the inferior fornix is gently removed with a spear.
4. Schirmer strips (35 mm x 5 mm size filter paper strip) will be placed in each eye at the junction of the middle and lateral thirds of the lower eye lid.
5. Under ambient light, the participant will be instructed to look forward and to blink normally during the course of the test. The test should be performed in a room with no direct air on the participant's face.
6. The Schirmer strips should remain in place until five minutes have elapsed or both strips have reached maximum score.
7. After five minutes, strips will be removed from both eyes and the amount of wetting will be recorded. The strips should be taped to the CRF.

Schirmer test using cotton swab nasal stimulation

At the Screening Visit, the Schirmer test should be performed using cotton swab nasal stimulation. New anesthetic drops should be instilled following the same procedure specified in steps #1 to #3 in the Basal Schirmer Test section.

1. With new strips in place, the examiner should insert cotton swabs in the participant's two nostrils simultaneously and gently probe both nasal middle turbinates for approximately 30 seconds. After this, the examiner can simply hold the swabs in place, applying gentle pressure, and repeat probing intermittently as necessary.

2. Alternatively, the participant can be instructed to hold the cotton swabs and gently probe both nasal turbinates simultaneously, resting intermittently before probing again. The examiner should continuously coach the participant on how to perform this test properly.
3. The Schirmer strips should remain in place until five minutes have elapsed or both strips have reached maximum score.

Both Schirmer scores will be recorded and it should be verified that the inclusion criteria have been met.

[figure not shown]

Figure 3 Target area of cotton swab nasal stimulation

Schirmer test during device application

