At Visit 3, the Schirmer test should be performed using the device. New anesthetic drops should be instilled following the same procedure specified in the Basal Schirmer Test section.

1. With new strips in place, the examiner should instruct the participant to fully insert the device in the nasal cavity and use the device for approximately 3 minutes. As needed, the examiner should continuously coach the participant on how to use the device properly.
2. The Schirmer strips should remain in place until five minutes have elapsed or both strips have reached maximum score.

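### AE capture opens at CAE entry, after the Screening Schirmer tests whose reactions Section 9.6 lists as potential AEs

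*Combined protocol and SAP*

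**What the plan says.** - **Start of capture.** Section 9.0: "The capture of AEs will begin with the", completed by the participant's arrival in the CAE. The first CAE session is Visit 2, Day 0 (Section 8.5.1).
- **Definition.** The same paragraph describes an AE as something "temporally associated with the use of an investigational product but not necessarily related to the investigational product". Section 8.2 places the first stimulation inside the Day 0 CAE session.
- **Anticipated events.** The second list in Section 9.6 is introduced by "The following is a list of potential AEs associated with the testing procedures at Screening or with CAE exposure". Its entries include "With the Schirmer test, corneal irritation and abrasion" and "With use of proparacaine, temporary burning, stinging and conjunctival redness of the eyes", and also a rare hyperallergic corneal reaction to proparacaine.
- **Screening tests.** Section 15.2.4: "At the Screening Visit, the Schirmer test should be performed using cotton swab nasal stimulation". Fresh anaesthetic drops are instilled for this test, and afterwards "Both Schirmer scores will be recorded and it should be verified that the inclusion criteria have been met". I read this as a basal and a swab-stimulated test at the same visit.
- **Later test.** "At Visit 3, the Schirmer test should be performed using the device". This is Day 7, after capture has opened.
- **Safety analysis.** The primary safety endpoint counts device-related AEs (Section 11.9), and the Safety population requires at least one device application (Section 11.4).

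**The concern.** The protocol foresees reactions to its own Screening procedures and calls them potential AEs, but its start rule opens the AE record only after Screening. A site following Section 9.0 literally would not record a Schirmer abrasion or a proparacaine reaction that cleared before Day 0, nor one in a person who never reached the CAE. The same reaction at Visit 3 would be recorded. What is at stake is the completeness and consistency of procedure-related safety data, including data on people who consented and were tested but did not go on to receive the device.

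**Working it through.** The plan states no figure on this point, so there is none to reproduce. The check compares passages and adds a simple count for scale.

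**1. Timing.** Screening is Day -21 ± 20 (Section 8.5.1): -21 - 20 = -41 and -21 + 20 = -1. Screening procedures therefore fall 1 to 41 days before Day 0, the earliest point at which capture can open.

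**2. Who is outside the window.**
- Qualified participants whose reaction resolves before Day 0. A reaction still present at CAE entry is inside.
- Screen failures who had the tests. From Section 5.1, 125 - 60 = about 65 people at most (65/125 = 52% of those screened). The lower bound is 0, because the Screening Visit instructions review eligibility test by test and people may fail before any Schirmer test.

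**3. Exposure count (test sessions, not events).**
- Screening, two tests each: 60 × 2 = 120 (qualified only) to 125 × 2 = 250 (everyone screened completes both).
- Visit 3, if all 60 attend: 60 × 1 = 60 (device test only) to 60 × 2 = 120 (same-day basal test as well).
- Share before the window: 120/(120 + 120) = 50%; 120/(120 + 60) = 67%; 250/(250 + 120) = 68%; 250/(250 + 60) = 81%.

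The 67% and 81% figures assume one Schirmer test at Visit 3. Section 11.8 analyses a Day 7 difference, and Section 15.2.4 calls for new drops and new strips at that visit. Together these point towards two tests, which gives 50% to 68%. Further tests in the redacted visit lists would lower the share.

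**4. Other routes into the record.**
- Section 9.1 treats any clinically relevant worsening of a finding as a recordable AE, with no start date and no device-use condition. An abrasion seen on examination would fit.
- Section 9.2 defines an SAE without tying it to product use, and Section 9.5 requires SAEs to be reported within 24 hours.
- Section 9.5 asks for all AEs during the study, although the term carries its Section 9.0 meaning.
- Section 8.3 records each medication with its reason, so a treated reaction leaves a trace.
- Section 8.5.2 requires AE assessment at any unscheduled visit.
- Section 15.2.1 has a clinically significant acuity loss since Screening evaluated as a potential AE. Acuity is tested at the beginning of each visit, so at Visit 2 this comes before CAE entry.
- Section 5.6 and the Early Termination section provide for the AE form where applicable, and for safety evaluations at discontinuation.

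None of these changes the Section 9.0 start point or names Screening. What they leave uncovered is mainly mild, transient, untreated reactions.

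**The case against.** The strongest reply is that opening capture at the experimental session is a stated choice. Section 9.6 is a risk list that supports the anticipated/unanticipated judgement; it is not a recording rule, and its Schirmer and proparacaine entries are needed for Visit 3 in any case. The routes above would pick up most reactions that matter clinically. The Screening Visit list and the Safety Measures are redacted and the Appendix 1 schedule is not in the text, so an AE query at Screening may exist.

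Much of this stands, and it limits the point. It does not remove it. The Section 9.6 list names Screening procedures explicitly. The other routes conflict with the Section 9.0 start rule and leave sites to choose between them. A Screening AE query, if there is one, would itself need reconciling with Section 9.0.

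A reader might infer that the product-use wording in the AE definition is a second, independent bar, so that an earlier start date alone would achieve nothing. The documents do not support that. Capture already opens before the first stimulation, Section 11.1 allows for people who never reach the application threshold in the CAE, and Section 9.6 treats reactions to procedures and to CAE exposure as potential AEs. The wording is loose and worth tidying, but the start date is the operative problem.

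**Conclusion.** The point holds as a minor inconsistency. Under the Section 9.0 start rule, Screening-procedure reactions that resolve before Day 0, or that occur in screen failures, fall outside AE capture, while identical reactions at Visit 3 fall inside. In scale, two anaesthetised tests per fully tested person, about 120 to 250 in all, take place before the window, and between 0 and about 65 screen failures may be affected.

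Two further inferences should be resisted. The 50% to 81% range is not a share of lost events: it counts tests, its upper end assumes that all 125 people complete both Screening tests and that Visit 3 has only one, and the documents give no reaction rate. Nor is the safety conclusion about the device compromised, because the primary safety endpoint, the Safety population and the effectiveness analysis do not depend on these events.

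The conclusion rests on the visible text of Sections 9.0, 9.6 and 15.2.4, and on reading the two Screening scores as basal and stimulated. Confidence is moderate because of the redactions.

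**What to change.** In Section 9.0, start AE capture at signed consent or the first study procedure for everyone screened, including those who do not qualify. Add study procedures to the AE definition so that it agrees with Section 9.6. List pre-device events separately under the existing *Not applicable* relationship category in Section 9.3. That category may have been meant only for people in the CAE before application, but it can hold these events without a new code. Bring the visit lists and Appendix 1 into line with the revised start point. Leave the device-related primary safety endpoint and the Safety population unchanged.

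The cost is a short text change and some additional AE forms for Screening events, in a number that the documents do not allow to be estimated.

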9.1 Adverse Event Recording

All AEs spontaneously reported by the participant and/or in response to an open question from study personnel or revealed by observation, physical examination or other diagnostic procedures will be recorded on the appropriate pages of the CRF. Any clinically relevant deterioration in clinical finding is considered an AE and should be recorded. When possible, signs and symptoms indicating a common underlying pathology should be noted as one comprehensive event.

9.2 Adverse Event Evaluation

The Investigator should evaluate if each AE is serious, related to the investigational device and anticipated using the following definitions.

A serious adverse event (SAE) is defined as any untoward medical occurrence that:

- It results in death (i.e., the AE actually causes or leads to death);
- It is life threatening (i.e., the AE places the participant at immediate risk of death);
- It requires or prolongs inpatient hospitalization. If a participant is hospitalized to undergo a medical or surgical procedure as a result of an AE, the event responsible for the procedure, not the procedure itself, should be recorded as the event. For example, if a participant is hospitalized to undergo coronary bypass surgery, the heart condition that necessitated the bypass should be recorded. Hospitalizations for diagnostic or elective surgical procedures or

hospitalizations required to allow outcome measurement for the study should not be recorded as SAEs:

- It results in persistent or significant disability/incapacity (i.e., the AE results in substantial disruption of the participant's ability to conduct normal life functions);
- It results in a congenital anomaly/birth defect in a neonate/infant born to a mother exposed to the investigational device;
- It is considered a significant medical event by the investigator based on medical judgment (e.g. may jeopardize the participant or may require medical/surgical intervention to prevent one of the outcomes listed above);
- It is considered sight-threatening by the Investigator.

9.3 Relationship of the AE to the investigational device

Definite	A clear cut causal relationship with the study device and no other possible cause
Probable	A causal relationship with the study device is likely although alternate etiologies are also possible
Possible	A causal relationship with study device is not definite, alternate etiologies are also possible
Not related	The AE has no causal relationship to study device and/or there is evidence of alternative etiology such as concurrent medication or illness.
Not applicable	The participant has not been exposed to the study device.

The AE will be determined to be device-related, making it an adverse device effect (ADE), if it is identified to have had a definite, probable or possible causal relationship to the investigational device.

An AE is unanticipated if the nature, severity, or frequency of the event is not consistent with either the known or foreseeable risk of AEs associated with the procedures involved in the research that are described in (a) the protocol-related documents, such as the IRB-approved research protocol, user manuals and the current IRB-approved informed consent document, and (b) other relevant sources of information such as product labeling and package inserts; or the expected natural progression of any underlying disease, disorder, or condition of the participant(s) experiencing the AE and the participant's predisposing risk factor profile for the AE.

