11.4 Evaluability of Data

All participants who initiated at least one study application will be eligible for inclusion in the analyses. Participation in the study will be summarized by presenting the number of participants who were enrolled, the number of participants who completed the study, and the number of participants who did not complete the study due to not reaching the threshold or by reason of early discontinuation.

Full Analysis Set Population (FAS): The FAS population will include all participants who initiated at least one application of the TrueTear device at any point during the study.

Per protocol population (PP): The PP population is a subset of the FAS population, which did not have a major protocol deviation likely to seriously affect the primary outcome of the study. This population will be the secondary population for the effectiveness analyses and will also be used to summarize the primary and exploratory effectiveness variables. If the PP and FAS populations are exactly the same, then additional efficacy analyses on the PP population will not be performed.

Safety Population: The safety population will be the same as the FAS population.

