11.9 Safety Analyses

The safety analyses will be performed for the Safety population. The primary safety endpoint will be the proportion of participants who experience one or more device-related AEs for each application and overall. The proportion and exact 95% confidence interval will be computed. Any changes in corrected distance visual acuity or slit lamp biomicroscopy findings will be summarized.

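### Section 9.3: the causality grades overlap, so an AE the device may have caused can be rated *Not related* and drop out of the primary safety endpoint

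*Combined protocol and SAP*

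**What the plan says.** Section 9.2 tells the investigator to judge relatedness with the definitions that follow, so the table in section 9.3 governs. Its grades include:

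- *Probable* is worded as follows: "A causal relationship with the study device is likely although alternate etiologies are also possible". This grade counts as device-related.
- *Possible* is worded as follows: "A causal relationship with study device is not definite, alternate etiologies are also possible". This grade counts too.
- *Not related* is worded as follows: "The AE has no causal relationship to study device and/or there is evidence of alternative etiology such as concurrent medication or illness". This grade does not count.

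*Definite* requires that there be no other possible cause, and *Not applicable* is for participants never exposed to the device. An event is device-related, and so an adverse device effect (ADE) in the protocol's terms, "if it is identified to have had a definite, probable or possible causal relationship to the investigational device".

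Section 11.9 builds the main safety result on that status: "The primary safety endpoint will be the proportion of participants who experience one or more device-related AEs for each application and overall". On precision it adds: "The proportion and exact 95% confidence interval will be computed". The denominator is set in section 11.4: "Safety Population: The safety population will be the same as the FAS population". Under section 9.5, serious events and ADEs go to the sponsor in writing within 24 hours.

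**The concern.** A causality scale should give one answer for one set of facts. Here the presence of another candidate cause is allowed under two grades that count towards the endpoint and is sufficient for the one grade, among exposed participants, that does not count. Two investigators could grade the same event differently and both follow the protocol.

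The conflict arises where events are expected. Section 9.6 lists headache (including migraine), sneezing, rhinorrhea and "Temporary aggravation of nasal allergies" among the potential device events. All of these have common background causes. Section 8.3 has every concurrent medication recorded, so a competing explanation will often be on file.

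The grade is the only route into the primary safety endpoint. The study is open-label with a single arm (section 4.0), so neither masking nor a control rate would show inconsistent attribution. The only by-site summary specified in the visible text is for the primary effectiveness endpoint (section 11.8). For non-serious events, the same grade decides whether the 24-hour report is due.

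**Working it through.** The plan states no adverse event rate, safety threshold or safety sample size, so there is no figure of its own to reproduce. The check is a comparison of definitions, followed by an illustration on assumed counts.

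**Step 1. How each grade treats another cause (section 9.3).**

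| Grade | Another cause present | Device-related? |
|---|---|---|
| *Definite* | Excluded | Yes |
| *Probable* | Allowed | Yes |
| *Possible* | Allowed | Yes |
| *Not related* | Sufficient by itself, through and/or | No |

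**Step 2. A test case.** A participant with migraine has a headache after an application and also reports a usual trigger that day. A device contribution cannot be excluded. *Definite* fails because another cause exists. *Possible* is met, or *Probable* if the device is thought likely. *Not related* is also met, through its second limb. The visible text has no tie-break.

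**Step 3. Consequence.** Graded *Possible* or *Probable*, the event is an ADE: it counts under section 11.9 and needs the 24-hour report under section 9.5. Graded *Not related*, it does not count and, if non-serious, needs no such report.

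**Step 4. When the endpoint moves.** The overall endpoint counts participants with at least one device-related event. A regraded event changes it only for a participant who has no other device-related event. Each such participant moves it by 1/N; with N = 60 (the approximate enrolment in section 11.1), 1/60 = 1.7 percentage points.

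**Step 5. Illustration.** The counts x are assumptions. The exact (Clopper-Pearson) 95% limits are the 2.5% quantile of Beta(x, N − x + 1) and the 97.5% quantile of Beta(x + 1, N − x). The starting point is 12 participants with a device-related event. Each participant moved out has no other such event.

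| Assumed change | x/N | Proportion | Exact 95% CI |
|---|---|---|---|
| None | 12/60 | 20.0% | 10.8 to 32.3 |
| 3 moved out | 9/60 | 15.0% | 7.1 to 26.6 |
| 6 moved out | 6/60 | 10.0% | 3.8 to 20.5 |
| 9 moved out | 3/60 | 5.0% | 1.0 to 13.9 |
| 12 moved out | 0/60 | 0% | 0 to 6.0 |
| 3 moved in | 15/60 | 25.0% | 14.7 to 37.9 |

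With N = 45, the target for the Day 45 application, 12/45 = 26.7% (14.6 to 41.9) and 6/45 = 13.3% (5.1 to 26.8).

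The last row of the table covers the opposite error. Read literally, *Possible* is loose enough to take in three participants whose events the device did not cause. The exact interval reflects sampling error only and does not cover misgrading in either direction.

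**The case against.** The best defence is that evidence of an alternative cause is a higher bar than an alternative being merely possible, so a careful investigator could keep the grades apart. That is a sensible reading, but the text does not require it and gives no rule for an event that has evidence of another cause and a plausible device contribution.

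The consequences are also bounded, and these points stand:

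- Section 11.9 attaches no test, threshold or stopping rule to the proportion.
- All adverse events are recorded whatever their grade (sections 9.1 and 9.5), so an all-causality table remains possible.
- Serious events are reported within 24 hours regardless of relatedness.
- Visual acuity and slit-lamp changes are summarised without a causality filter.
- At most two sites take part, which limits inconsistency between sites.
- The safety measures in section 6.2 and many eligibility criteria are redacted. Further safety summaries may exist, and the number of participants with confounding conditions cannot be judged.

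A reader might also infer three stronger claims that the documents do not support:

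- *The endpoint will be understated.* An overlap lets the grader go either way. The loose wording of *Possible* can admit unrelated events as well.
- *Aggravated nasal allergy always qualifies as Not related.* The event is the aggravation. A pre-existing allergy is a susceptibility and is not in itself evidence that something other than the device caused the worsening. Such events readily raise the conflict; they do not settle it.
- *Every regraded event costs 1.7 points.* That holds only under the condition in Step 4.

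**Conclusion.** The definition of *Not related* is wrong as written. It overlaps with two grades that count as device-related, and no visible rule resolves the overlap. The text therefore permits an event that the device may have caused to be left out of the primary safety endpoint and, if non-serious, out of 24-hour ADE reporting. This follows from the wording alone and needs no assumption about event rates.

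The size and net direction of the effect cannot be derived from the documents. The illustrated fall from 20.0% to 10.0% depends on assumed counts, on 60 treated participants, and on the regraded participants having no other device-related event. The endpoint can still be computed, but its main input is ambiguously defined. That deserves correction and does not call the design into question.

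**What to change.** In section 9.3, replace the definition of *Not related* with: *There is no reasonable possibility of a causal relationship to the study device; evidence of an alternative etiology does not by itself exclude a relationship.* Add that when a device contribution cannot be excluded, the event is graded *Possible* or *Probable* according to its likelihood. Carry both statements into the adverse event CRF instructions.

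Two shorter repairs should be avoided:

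- Replacing and/or with and would make *Not related* require both limbs. A clearly unrelated event with no identified cause could then not be graded *Not related*.
- Sending every event with an alternative cause to *Possible* would contradict *Probable*, which already covers a likely device cause with alternatives present.

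The cost is a short edit to section 9.3 and the CRF instructions, with no change to design, sample size or procedures. The device-related proportion may be somewhat higher, and a few more events may need a 24-hour report.
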